2.3 POTENTIAL RISKS AND BENEFITS

2.3.1 KNOWN POTENTIAL RISKS

GRF6021, a 5% human plasma protein fraction, is reduced in coagulation factors and gamma globulins and serves as a viable source of soluble, infusible plasma proteins from healthy male and female donors.

GRF6021 has been marketed since 1958 in the US, is approved in other parts of the world, and has a well-established safety profile with a very low frequency of reported infusion reactions (0.002%) ([PSUR](#)). Based on the cumulative review of post-marketing safety surveillance data ([PSUR](#)), the benefit-risk balance for GRF6021 as an investigative product in individuals undergoing THA or TKA is favorable. Because it has been depleted of the majority of immunogenic proteins, GRF6021 is not expected to alter the blood typing characteristics of the recipient and should not sensitize humans to its subsequent administration ([Bertrand 1959](#)). ABO antigen typing is not required prior to administration. Finally, the additional steps taken during production to remove viral pathogens provide an increased margin of pathogen safety in comparison to fresh frozen plasma.

GRF6021 is not expected to significantly alter safety laboratory parameters, including urinalysis, coagulation times, prothrombin times, prothrombin consumption, platelet counts, or fibrinogen levels when given in quantities of up to 1000 mL ([Bertrand 1959](#)). Hypotension may occur, particularly following rapid infusion. The blood pressure may normalize spontaneously after the slowing or discontinuation of the infusion. Vasopressors will also correct the hypotension ([PI](#)). GRF6021 is contraindicated for use in patients on cardiopulmonary bypass as severe hypotension has been reported ([Bland 1973](#)). GRF6021 is contraindicated in patients with severe anemia, congestive heart failure, or increased blood volume ([PI](#)).

GRF6021 is made from human plasma and may carry a risk of transmitting infectious agents, e.g., viruses, the variant Creutzfeldt-Jakob disease (vCJD) agent, and, theoretically, the Creutzfeldt-Jakob disease (CJD) agent. The risk that GRF6021 can transmit an infectious agent has been reduced by screening plasma donors for prior exposure, testing donated plasma, and including manufacturing steps with the capacity to inactivate and/or remove pathogens.

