15. Clinically significant abnormalities on screening electrocardiogram (ECG) that in the opinion of the investigator could put the subject at risk, including QTc intervals (using Fridericia's correction formula) of ≥ 450 ms in men and ≥ 470 ms in women.
16. Current, active liver disease: > 3-fold elevation of liver enzymes (alanine aminotransferase (ALT)

- and aspartate aminotransferase (AST) over upper limit of normal.
17. Clinically significant abnormalities in complete blood count (CBC), complete metabolic panel, serum albumin, or coagulation.
 18. History of a major infection (e.g. bacterial pneumonia) in the last 3 months, or recent minor infection (e.g. influenza, urinary tract infection) or fever (measured body temperature above 100.5 degrees F on 2 consecutive days) that in the assessment of the Principal Investigator could interfere with the primary endpoint.
 19. Severe anemia (hemoglobin < 8 g/dL).
 20. Urine protein-to-creatinine ratio (UPCR) of > 1.5 grams of protein per gram of creatinine.
 21. Inadequate venous access to allow IV drug delivery or multiple blood draws.
 22. Concurrent participation in any other therapeutic treatment trial. If there was prior clinical trial participation, subject must have discontinued investigational agents for at least 30 days for small molecules, and 1 year for active or passive immunotherapies prior to screening.
 23. Current diseases associated with significant alterations in immune function, including, but not limited to, autoimmune disease and cancer, except adequately-treated squamous or basal-cell carcinoma.
 24. Ongoing immunosuppressant treatment or within 5 half-lives of the treatment.
 25. History of substance abuse (alcohol, drugs of abuse) in the last 2 years.
 26. Functional impairment of major joint or lower extremity other than joint undergoing surgery.
 27. Any other condition and/or situation that the investigator believes may interfere with the safety of the subject, study conduct, or interpretation of study data.

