7.1.1.2.6 Blood and Urine Collection for Laboratory Evaluations

In addition to screening evaluations (see [Section 7.1.1.1.6](#)), subjects will have blood and urine specimens collected for clinical evaluation (see [Section 7.2.1 Clinical Laboratory Evaluations](#)). Refer to [Section 15 Schedule of Events](#) for timing and frequency of blood and urine collection for laboratory evaluations.

The following labs will be performed within ~48 hours after the end of the infusion on Day 3 (exit lab panel):

- Infectious serology (anti-HIV antibodies, anti-hepatitis B surface antigen, anti-hepatitis B core antigen, anti-hepatitis C antibodies), direct antiglobulin test, RBC antibody screen (including direct Coombs and anti-RBC antibody).
- ALT, AST, bilirubin (total), ionized calcium, chloride, creatinine, potassium, protein total, sodium, blood urea nitrogen, PTT, PT/INR.
- CBC with differential (basophils, eosinophils, lymphocytes, monocytes, neutrophils).
- Urinalysis: blood, glucose, ketone, protein, pH, specific gravity, nitrite, leukocytes, urine creatinine, urine protein, urine protein/creatinine ratio, and reflex urine microscopy if indicated.
- Pregnancy test.

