7.3 STUDY SCHEDULE

7.3.1 SCREENING

Visit 1, Screening Visit (Day -42 to -3)

- Informed consent of subject as documented by a signed and dated informed consent form that must be obtained prior to any study-related assessments.
- Collect demographic information.
- Review subject's current and prior medications, including opioid consumption assessment.
- Collect vital signs, height, and weight.
- Physical exam.
- Collect blood and urine samples required for Screening (including pregnancy test for WOCBP).
- Provide subject with ActiGraph wearable device and any training required for use of the device (the ActiGraph can also be mailed to the subject 1 week before the scheduled surgery).

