7.3.4 BASELINE: ON-SITE/TREATMENT

The on-site Baseline assessments will be gathered prior to the first infusion on Day 1. After the first infusion on Day 1, the subject will be discharged from the facility and come back the following morning (Day 2) for the inpatient period. The inpatient treatment period is 2 days during which each subject will receive 3 additional doses of 250 mL of their assigned treatment allocation (i.e., either GRF6021 or placebo).

Visits 3 through 5, Treatment (Days 1-3):

- Perform the following procedures on each day *prior* to administering (the first) study infusion:
 - Review AEs and concomitant medications.
 - 12-lead ECG (**Day 1 and 3 Only**).
 - Collect sample for CyTOF assessment (**Including second infusion on Day 2**).

- Obtain samples for proteomic assessments; fasting samples preferred (**Including second infusion on Day 2**).
- Collect vital signs (BP, HR, RR, and body temperature) (**Including second infusion on Day 2**).
- Targeted physical exam (**Day 1 and 3 Only**).
- Pregnancy testing for WOCBP (**Day 1 Only**).
- Administer 3D-CAM, SRS, and WOMAC (**Day 1 and 3 Only**).
- ActiGraph device data collection (**Day 1 and 3 Only**).
- Administer study treatment per the GRF6021 Infusion Administration Manual:
 - On the day before surgery (**Day 1**).
 - On the day of surgery within 4 hours before surgery start (first incision) (**Day 2**).
 - On the day of surgery upon arrival in the PACU (within 5 hours after the first incision) (**Day 2**).
 - On the day after surgery (**Day 3**).
- Perform the following assessments following each infusion start:
 - BP and HR at 15, 30, 45, and 60 min after infusion start.
 - Body temperature and RR at 60 minutes.
 - Collection of perioperative data (**Day 2 Only**, after second infusion).
 - Opioid consumption assessment (**Days 2 and 3 Only**).
 - 12-lead ECG (**Day 3+1 Only**, after end of last infusion).
 - Exit lab panel including pregnancy test (**Day 3 Only**, after end of last infusion).
 - Administer 3D-CAM (**Day 2 Only**, after second infusion).

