18 REVISION HISTORY

18.1 SUMMARY OF CHANGES

Protocol Version 3.0 dated 14NOV2019
Replaces: Protocol Version 2.0 dated 15APR2019

In this table, changes from Version 3.0 dated 14NOV2019 are described and the rationale for each revision is provided.

Location	Description	Purpose
Throughout	Previously read: V2.0_15APR2019 Now reads: V3.0_14NOV2019	Version Control
Throughout	Removed mention of Ethics Committee(s).	This study is only taking place in the United States with one Investigational Review Board.
Throughout	Previously read: Secondary efficacy endpoints Now reads: Secondary endpoints	Secondary endpoints include assessments for safety as well as efficacy.
Section 4.2.2.	Added: End of study treatment comparison of the Western Ontario and McMaster Universities Osteoarthritis Index (WOMAC) (Bellamy 1986, Bellamy 2002)(Appendix 3). Clarified time to score of WOMAC is only for a subset of questions.	Updated per revised timepoints in Section 15.1.
Section 7.1.1.3.4 and 17	Revised for the full WOMAC to be completed at Baseline (Visit 2) and End of Study (Visit 15). A subset of questions from the WOMAC to be completed during interim visits per Section 15.1.	Updated per the revised timepoints in Section 15.1.
Section 5.2	Previously read: Exclusion Criteria #1 Blood coagulation disorders, including severe liver disease, vitamin K deficiency, von Willebrand disease, hemophilia A or B or other known deficiencies in clotting factor (fibrinogen, prothrombin, factor VII, X, XI, XII, or XIII). Now reads: Exclusion Criteria #1 Blood coagulation disorders, including severe liver disease, vitamin K deficiency, von Willebrand disease, hemophilia A or B or other known deficiencies in clotting factors (fibrinogen, prothrombin, factor VII, X, XI, XII, or XIII) that in the opinion of the investigator could put the subject at risk.	GRF6021 does not contain coagulation factors, and the volume of GRF6021 given to subjects in this trial will not cause hemodilution and secondary coagulopathy. Thus, the sentence was modified to clarify that the PI should use his/her clinical judgement to assess whether a coagulation disorder may put the subject at risk.

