Section 5.2	Removed: Exclusion Criteria #14 History of Torsades de Pointes dysrhythmia.	GRF6021 is not associated with any known effects on ECG or electrolytes or any cardiac risk. Thus, The PI should use his/her clinical judgement to determine whether an ECG abnormality would warrant the exclusion of the subject.
Section 5.2	Previously read: Exclusion Criteria #15 Clinically significant abnormalities on screening electrocardiogram (ECG) including QTc intervals (using Fridericia's	GRF6021 is not associated with any known effects on ECG or electrolytes or any cardiac risk.

	
correction formula) of ≥ 450 ms in men and ≥ 470 ms in women.
 
Now reads: Exclusion Criteria #15 Clinically significant abnormalities on screening electrocardiogram (ECG) that in the opinion of the investigator could put the subject at risk, including QTc intervals (using Fridericia's correction formula) of ≥ 450 ms in men and ≥ 470 ms in women.
	Thus, The PI should use his/her clinical judgement to determine whether an ECG abnormality would warrant the exclusion of the subject.
Section 5.2	
Previously read: Exclusion Criteria #19 History of a major infection (e.g. bacterial pneumonia) in the last 3 months, or minor infection (e.g. influenza, urinary tract infection) or fever (measured body temperature above 100.5 degrees F on 2 consecutive days) in the last 1 month.
 
Now reads: Exclusion Criteria #18 History of a major infection (e.g. bacterial pneumonia) in the last 3 months, or recent minor infection (e.g. influenza, urinary tract infection) or fever (measured body temperature above 100.5 degrees F on 2 consecutive days) that in the assessment of the Principal Investigator could interfere with the primary endpoint.
	The PI should use his/her clinical judgment to determine whether the infectious or inflammatory process was systemic, in which case there may be effects on the primary endpoints.
Section 5.2	
Previously read: Exclusion Criteria #20 Hemoglobin < 9 g/dL in women and < 10 g/dL in men.
 
Now reads: Exclusion Criteria #19 Severe anemia (hemoglobin < 8 g/dL).
	GRF6021 is contraindicated in severe anemia because of the risk of hemodilution; however, there is no known risk in mild or moderate anemia.

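### The protocol calls GRF6021 contraindicated in severe anemia, but requires no post-operative hemoglobin result before infusions 3 and 4

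*Protocol*

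**What the plan says.** - **Contraindication.** Protocol 2.3.1: "GRF6021 is contraindicated in patients with severe anemia, congestive heart failure, or increased blood volume". It is not limited to the time of entry.
- **Threshold.** Exclusion 19 in 5.2: "Severe anemia (hemoglobin < 8 g/dL"). This is an entry criterion. The rationale for it in 18.1 is "GRF6021 is contraindicated in severe anemia because of the risk of hemodilution; however, there is no known risk in mild or moderate anemia".
- **First required count.** The screening panel includes a CBC: "Visit 1, Screening Visit (Day -42 to -3").
- **Second required count.** The exit panel, in 7.1.1.2.6, also includes a CBC: "The following labs will be performed within ~48 hours after the end of the infusion on Day 3 (exit lab panel"). The Schedule of Events marks the screening panel at Visit 1 only and the exit panel at Visit 5 only.
- **Infusions after surgery.** Surgery is on Day 2. Infusion 3 is given "On the day of surgery upon arrival in the PACU (within 5 hours after the first incision"), and infusion 4 on the following day.
- **Checks before infusions 3 and 4.** Section 7.3.4 lists vital signs and blood for CyTOF ("Collect sample for CyTOF assessment") and proteomics before both. Before infusion 4 it adds review of adverse events and medications, an ECG and a targeted examination. Hemoglobin is not listed.
- **Dose holding.** Sections 5.4, 6.1, 7.3.4 and 8.5 contain no hemoglobin-based rule for withholding an infusion.

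**The concern.** Arthroplasty is the one foreseeable bleeding event in the trial, and it falls between the last required blood count and infusions 3 and 4. That count may be about six weeks old by the day of surgery. A subject who entered just above 8 g/dL could be below it in the PACU. The protocol, followed as written, would give two more doses of a product it calls contraindicated in that state without requiring anyone to look.

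What is at stake is mainly subject safety. There is also a smaller interpretive loss. From the required counts alone, a low exit hemoglobin cannot be placed before or after infusions 3 and 4, so its relation to dosing cannot be judged.

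**Working it through.** The plan gives no figure to reproduce. The first step sets the timings side by side. The second and third steps illustrate size.

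**1. Required counts against doses**

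| Event | Timing | Blood count required? |
|---|---|---|
| Screening | Day -42 to -3 | Yes |
| Infusion 1 | Day 1 | No |
| Infusion 2, then surgery | Day 2 | No |
| Infusion 3 | Day 2, within 5 hours of first incision | No |
| Infusion 4 | Day 3 | No |
| Exit panel | Within about 48 hours after infusion 4 | Yes |

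Required counts between surgery and infusion 3: none. Between surgery and infusion 4: none. The early-termination exit panel (7.3.7) is for subjects leaving the study and does not gate a dose.

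**2. Which entry values could fall below 8 g/dL by the time of infusion 3**

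Inputs: blood volume V = 5,500 mL (Protocol Table 1). Blood loss L is not given in the documents, so 300 to 1,000 mL is assumed, replaced by red-cell-free fluid, with no transfusion. R is the volume retained from infusions 1 and 2 (500 mL given). Section 2.2 says up to 80% of a crystalloid can leave the vessels, so at 20% kept R = 100 mL for saline. For colloid the upper extreme is R = 500 mL.

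Hemoglobin after surgery = entry value × V/(V+R) × exp(−L/(V+R)). Setting this to 8 gives:

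entry cut-off = 8 × (V+R)/V × exp(L/(V+R))

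| Retained before surgery | L = 300 mL | L = 500 mL | L = 1,000 mL |
|---|---|---|---|
| R = 0 (study fluid ignored) | 8 × exp(300/5500) = 8.4 | 8.8 | 9.6 |
| R = 100 mL (saline, 20% kept) | 8 × (5600/5500) × exp(300/5600) = 8.6 | 8.9 | 9.7 |
| R = 500 mL (colloid, all kept) | 8 × (6000/5500) × exp(300/6000) = 9.2 | 9.5 | 10.3 |

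Subjects entering between 8.0 g/dL and the cut-off would be below 8 before infusion 3 under that row's assumptions.

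**3. What the study dose itself adds, starting from 8.0 g/dL**

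Hemoglobin = 8 × V/(V + retained volume).

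- Colloid, all kept: one dose, 8 × 5500/5750 = 7.65; two doses, 8 × 5500/6000 = 7.33.
- Saline, 20% kept: one dose, 8 × 5500/5550 = 7.93; two doses, 8 × 5500/5600 = 7.86.
- Excess of GRF6021 over placebo: at most about 0.28 g/dL for one dose and 0.52 g/dL for two.

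This step adds the dose on top of full replacement. If infusion 3 is part of the replacement fluid, the added dilution is smaller.

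**The case against.** The case against has real weight.

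- **The product is described as benign at this volume.** Section 2.3.1 expects no significant change in safety laboratory parameters at quantities up to 1,000 mL, which is the trial's total dose. Section 2.2 reports good tolerability from 250 mL to 1.5 L. Section 18.1 says "the volume of GRF6021 given to subjects in this trial will not cause hemodilution and secondary coagulopathy".
- **There is a route to hold a dose.** The investigator must judge out-of-range laboratory values (7.2.1). Adverse events are reviewed before infusion 4. Holding treatment is a recordable action (8.4.1), and a subject can be withdrawn for unacceptable risk (5.4). Exclusions 17 and 27 can also keep out some borderline subjects.
- **Other documents govern the infusions.** They follow Stanford procedures for colloid infusions and the Infusion Administration Manual. Neither is among the documents, and either may contain a check. Routine hospital counts are not ruled out.
- **A hold need not prevent dilution.** Clinical fluids continue, and colloids are ordinary perioperative care.

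Much of this stands, and it limits the point to the protocol text. It does not remove the point, because none of the protocol measures is a hemoglobin value or requires one. The 2.3.1 statement on laboratory parameters does not name hemoglobin. Estimated blood loss is among variables that may be captured, but it is not tied to dosing.

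A reader might infer that the two statements in 18.1 contradict each other on hemodilution. The documents do not support that: the statement about the study volume explains the relaxed coagulation criteria and neither withdraws nor restates the anemia contraindication. A reader might also treat 8 g/dL as a dosing rule that the schedule breaks. No section makes it one.

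**Conclusion.** The point holds as a missing low-cost safeguard. The protocol states a contraindication, gives it a number at entry, and does not require that number to be checked after the operation most likely to bring a subject below it. This follows from the text and needs no modeling assumption, except that a CBC includes hemoglobin.

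The size is uncertain. The number of subjects affected cannot be derived, because the documents give neither the entry hemoglobin distribution nor the expected blood loss. The cut-offs of about 8.4 to 10.3 g/dL rest on the assumed loss, on replacement without red cells, and on the stated retention. They are illustrations and do not mark out the only subjects at risk.

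A reader might go further and infer that harm is to be expected, or that subjects were dosed in a contraindicated state. The documents support neither. The extra dilution over placebo is modest, no harm threshold is tied to it, and hospital practice or the manual may already cover the check.

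**What to change.** Add to Protocol 7.3.4 and the Schedule of Events a review of a post-operative hemoglobin before infusions 3 and 4. It can come from a rapid test on blood already drawn at Visits 4b and 5, or from a hospital count. Hold the study infusion if the value is below 8 g/dL unless the investigator documents a reason to proceed. Apply the same rule in both arms and leave clinical fluids and transfusion to the treating team. If the Infusion Administration Manual already has such a rule, cite it instead.

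Record the values and any held doses, and report them by arm. Keep subjects with a held dose in a supporting analysis of all randomized subjects with available CyTOF samples. This is workable: the Visit 5 sample precedes infusion 4, so holding that dose alters none of the four samples. Holding infusion 3 can alter only the Visit 5 sample. CyTOF Dataset 2 (Visit 3 to Visit 4a) is unaffected either way.

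Costs:

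- The result must be back in time for infusion 3, within 5 hours of first incision.
- Each subject with any held dose leaves the Evaluable set (Protocol 5.4.2, SAP 8.2), whether one dose or two are held: 1/40 = 2.5% of the planned number, 1/37 = 2.7% of the number reached. Section 5.4.2 allows replacement if the subject discontinues.
- Holds could be slightly more frequent on GRF6021, since a colloid expands blood volume more than saline. The supporting analysis is there to guard against arm-related exclusion.

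SAP 7.3 says enrollment has ended, so the dosing rule serves reuse of this protocol. For this trial, any perioperative hemoglobin values on record can still be tabulated by arm.

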5.3 STRATEGIES FOR RECRUITMENT AND RETENTION

The Sponsor does not anticipate any specific challenges in enrolling 45 subjects with the goal of obtaining at least 40 evaluable subjects in this study. Subjects will be recruited continuously until the planned sample size is achieved. Subjects who withdraw or are withdrawn during screening, as well as subjects who discontinue, may be replaced (see [Section 5.4.2](#)).

The expected length of participation in the study of approximately 7 to 12 weeks is not expected to be challenging to subjects. A description of the study will be included in local clinical trial databases, as required.

5.4 SUBJECT WITHDRAWAL OR TERMINATION

A subject may be withdrawn from the study for the following medical or administrative reasons:

- Occurrence of an adverse event (AE) that represents an unacceptable risk to the subject and when continued participation in the investigational study is not warranted, in the judgment of the investigator or Sponsor Medical Monitor. The investigator must follow the subject until the AE resolves or is stable, unless the subject is lost to follow up.
- Treatment with a prohibited concomitant medication other than the use of appropriate medications for the treatment of AEs under direction of the investigator.
- Subject noncompliance, defined as refusal or inability to adhere to the trial schedule or procedures.
- At the request of the subject (e.g., subject withdraws consent), investigator, Sponsor, or regulatory authority.
- Pregnancy.

5.4.2 HANDLING OF PARTICIPANT WITHDRAWALS OR TERMINATION

Subjects will be encouraged to complete the study and all assessments. Subjects may voluntarily withdraw at any time, and the investigator may discontinue individual subjects from the study at any time.

Approximately 45 subjects (1:1 ratio of GRF6021 to placebo) will be enrolled in the study with the aim of having 40 evaluable subjects. Evaluable subjects are those who received all 4 doses and had all blood draws for assessment of the primary endpoint. Subjects who discontinue or are unblinded may be replaced. Subjects who withdraw or are withdrawn during screening will be replaced.

